5.6.3. Additional Safety Assessments

5.6.3.1. Clinical Laboratory Tests

Descriptive statistics will be presented for all chemistry, hematology, and urinalysis laboratory tests at scheduled time points in the double-blind phase.

Change from baseline(DB) to all post-baseline visits in the double-blind phase will be summarized for chemistry, hematology, and urinalysis tests and displayed by study intervention group.

Shift in chemisty lab values from baseline to maximum post-baseline value will be summarized for the double-blind phase and displayed by study intervention group. Shift in Metabolic Lab values specifically from baseline to maximum post-baseline value will be summarized for the double-blind phase and displayed by study intervention group based on the following categories.

Glucose:

- from <100 mg/dL to [$\geq 100 \text{ mg/dL} <126 \text{ mg/dL}$] (normal to borderline)
- from $[\geq 100 \text{ mg/dL} <126 \text{ mg/dL}]$ to $\geq 126 \text{ mg/dL}$ (borderline to high)
- from <100 mg/dL to $\ge 126 \text{ mg/dL}$ (normal to high)

Triglycerides:

- from <150 mg/dL to $\geq 200 \text{ mg/dL}$ (normal to high/very high)
- from <150 mg/dL to $\geq 500 \text{ mg/dL}$ (normal to very high)
- from $[\geq 150 \text{ mg/dL} \langle 200 \text{ mg/dL}]$ to $\geq 200 \text{ mg/dL}$ (borderline to high/very high)
- from $[\geq 150 \text{ mg/dL} \langle 200 \text{ mg/dL}]$ to $\geq 500 \text{ mg/dL}$ (borderline to very high)
- from [$\geq 200 \text{ mg/dL} \langle 500 \text{ mg/dL}]$ to $\geq 500 \text{ mg/dL}$ (high to very high)

Total Cholesterol

- from <200 mg/dL to $\geq 200 \text{ mg/dL}$ (normal to borderline/high)
- from <200 mg/dL to $\geq 240 \text{ mg/dL}$ (normal to high)
- from <200 mg/dL to [$\geq 200 \text{ mg/dL} <240 \text{ mg/dL}$] (normal to borderline)
- from $\geq 200 \text{ mg/dL} \langle 240 \text{ mg/dL} \rangle$ to $\geq 240 \text{ mg/dL}$ (borderline to high)

HDL Cholesterol

• from \geq 40 mg/dL to <40 mg/dL (normal to low)

LDL Cholesterol

• from < 100 mg/dL to $\ge 160 \text{ mg/dL}$ (normal to high)

Clinical laboratory test values in the double-blind phase will be considered "treatment-emergent markedly abnormal" (TEMA) using the criteria defined by the sponsor listed in Section 6.8.

• If the postbaseline value is above the upper limit of the markedly abnormal criteria and the baseline(DB) value is equal to or below the upper limit, then the postbaseline marked abnormality will be considered TE. The same applies to the postbaseline value being below the lower limit of the markedly abnormal criteria with the baseline value being equal to or above the lower limit of the markedly abnormal criteria.

- Statistical Analysis Plan 42847922ALZ2001
- If the baseline(DB) value is missing, a postbaseline marked abnormality will always be considered as TE.

The number and percentage of participants with treatment-emergent markedly abnormal values in the double-blind phase will be presented by study intervention group.

The incidence of participants with treatment-emergent ALT values >3*upper normal limit (ULN) or AST value > 3*ULN will be presented for the double-blind phase. Additionally, incidence of treatment-emergent hepatic toxicity (suspected Hy's Law [U.S. Department of Health and Human Services, Food and Drug Administration, Center for Drug Evaluation and Research (CDER), Center for Biologics Evaluation and Research (CBER). [2009]] cases) defined as (ALT values >3*ULN or AST values > 3*ULN) AND total bilirubin values >2*ULN will be presented for the double-blind phase. Similar to the markedly abnormal analysis, only participants with baseline(DB) values that don't meet the criteria or are missing will be eligible for these analyses.

A listing of participants with treatment emergent markedly abnormal laboratory values will be provided. A listing of participants with ALT > 3* ULN or AST values > 3*ULN) and participants with hepatic toxicity (suspected Hy's Law cases) will be provided.

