	Minimum 2 weeks and up to 4 weeks prior to randomization ^p	Baseline	Remote contact ^f		Preferred onsite (remote optional) ⁱ	End of DB Treatment/Early Withdrawal	Remote optional ⁱ (2 weeks after completing the treatment period or after last dose if EW (EW FU 1)	Additional FU visit for EW of study drug ^k (remote optional) – EW FU 2, 3, 4
Study Day	D-28 to D-1	D1	D8	D15	D29	D43	D57	Every 2 weeks up to Day 57
Study Week			1	2	4	6	8	
Visit	1 ^s	2	3	4	5	6	7	
Visit window (Days)			±2	±3	±3	±3	+/-3	
Study Procedure								
SDI	Х	Х		Х	X	Х	Х	Х
CMAI-C		Х		Х		Х		
GDSI		Х				X		
Safety Assessments								
Physical examination	X	Х				X		
Neurological examination	X	Х				X		
Height	X							
Weight	X	Х				Х		
Vital signs ^c	X	Х		X		X	X°	X°
12-lead ECG ^c	X	Х				X		
C-SSRS	X	Х		Х	X	X	X	Х
PWC-20						X	X	
Cognition								
ADAS-Cog-14		Х		X		X		
Clinical Laboratory Tests								
Hematology, chemistry ^d	X	Х				Х		
Urinalysis	X	X				X		

Period	SCR	DB Treatment				FU		
	Minimum 2 weeks and up to 4 weeks prior to randomization ^p	Baseline	Remote contact ^f		Preferred onsite (remote optional) ⁱ	End of DB Treatment/Early Withdrawal	Remote optional ⁱ (2 weeks after completing the treatment period or after last dose if EW (EW FU 1)	Additional FU visit for EW of study drug ^k (remote optional) – EW FU 2, 3, 4
Study Day	D-28 to D-1	D1	D8	D15	D29	D43	D57	Every 2 weeks up to Day 57
Study Week			1	2	4	6	8	
Visit	1 ^s	2	3	4	5	6	7	
Visit window (Days)			±2	±3	±3	±3	+/-3	
Study Procedure								
Clinical Pharmacology Assessments								
Blood sample collection for PK ^j				Х		Х		
Alpha-1-acid glycoprotein				Х		Х		
Biomarkers								
Blood sample collection		Х				Х		
Genetic and								
Pharmacogenomic								
(DNA) Assessments								
Blood sample collection ^m		X						
Digital								
Actigraphy device instructions	Х	X		X				
Actigraphy device		Х		Х		Х		
performance check								
Actigraphy device		Continuous ^h						
measuremento								

Period	SCR	DB Treatment				FU		
	Minimum 2 weeks and up to 4 weeks prior to randomization ^p	Baseline	Remote contact ^f		Preferred onsite (remote optional) ⁱ	End of DB Treatment/Early Withdrawal	Remote optional ⁱ (2 weeks after completing the treatment period or after last dose if EW (EW FU 1)	Additional FU visit for EW of study drug ^k (remote optional) – EW FU 2, 3, 4
Study Day	D-28 to D-1	D1	D8	D15	D29	D43	D57	Every 2 weeks up to Day 57
Study Week			1	2	4	6	8	
Visit	1 ^s	2	3	4	5	6	7	
Visit window (Days)			±2	±3	±3	±3	+/-3	

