The off-body touchless sensor(s) will also be returned from the home subsequent to the last participant's study visit (in the subset of the participants who agreed for use of the device at screening).

At the start of the follow-up phase, further clinical/standard of care for the treatment of BPSD symptoms should be arranged by the study investigator and/or the participant's treating physician. The decision to continue and/or change the BPSD treatment in this phase will be at the discretion of the investigator and/or participant's treating physician.

Unscheduled visits

For unscheduled visits conducted for non-administrative/non-logistic reasons (eg., a safety event or change in the participant's BPSD condition), the minimum recommended evaluations/assessments include: physical and neurological examinations, vital signs, NPI-C, NPI-12, SDI, C-SSRS, hematology and chemistry laboratory tests. Additional examinations and scales can be performed as per the clinical judgement of the investigator and protocol requirements.

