7. DISCONTINUATION OF STUDY INTERVENTION AND PARTICIPANT DISCONTINUATION/WITHDRAWAL

7.1. Discontinuation of Study Intervention

A participant's study intervention must be discontinued if:

- The participant (or legal representative) withdraws consent to receive study intervention
- The investigator believes that for safety reasons or tolerability reasons (eg, AE) it is in the best interest of the participant to discontinue study intervention
- Based upon the clinical judgment of the investigator, a participant may be withdrawn for lack of efficacy (ie, clinically significant worsening of agitation/aggression or other BPSD symptoms).
- Noncompliance with study drug administration defined as missing either 4 or more consecutive doses of study drug or a total of 8 or more doses during any 4-week period
- The participant persistently uses a disallowed medication as discussed with the sponsor's medical monitor or designee.
- The participant shows signals of acute suicidal ideation with a clear plan or intent at any time during the study; the participant should be referred to appropriate medical/psychiatric care.
- AST and/or ALT exceeds 5X ULN (confirmed by repeat testing).
- AST and/or ALT exceeds 3X ULN and total bilirubin exceeds 1.5X ULN (confirmed by repeat testing).
- Study drug blind is broken during the DB treatment phase

Follow-up assessments should be obtained according to the SoA. All participants who discontinue study drug in the DB treatment phase, will have an Early Withdrawal visit (Visit 6 in the SoA) and a Follow-up visit (Visit 7 in the SoA). Participants who discontinue study drug prior to Day 35 are encouraged to continue after the Follow-up visit (Visit 7 in the SoA) with additional follow-up visits every 2 weeks per the SoA until Day 57. If a participant discontinues study medication and enters the follow-up phase, other concomitant medications, including disallowed medication, may be started (see Section 6.8.1). Study intervention assigned to the participant who discontinued study intervention may not be assigned to another participant. Additional participants will not be entered to replace participants who discontinue the study early.

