5. STATISTICAL ANALYSES

5.1. General Considerations

5.1.1. Visit Windows

As participants do not always adhere to the protocol visit schedule, the following rules are applied to assign actual visits to analysis visits. Listed below are the visit windows and the target days for each visit. The reference day is Study Day 1. If a participant has 2 or more actual visits in 1 visit window, the visit closest to the target day will be used as the protocol visit for that visit window. The other additional visit(s) will not be used in the summaries or

Statistical Analysis Plan 42847922ALZ2001

analyses, but they can be used for determination of clinically important endpoints. If 2 actual visits are equidistant from the target day within a visit window, the later visit is used.

All assignments will be made in chronological order. Once a visit date is assigned to a visit window, it will no longer be used for a later time point except for the endpoint. Listed below (Table 1) are the analysis visit windows and the target days for each visit defined in the protocol.

		Scheduled			Target
	Analysis	Visit	Time Interval	Time Interval	Time Point
Parameter	Phase	Number	(label on output)	(Day)*	(Day)*
NPI-12	SCR	1	Screening	<1	
SDI	DB	2	Baseline (DB)	<=1	1
C-SSRS		4	Day 15	2 to 22	15
_		5	Day 29	23 to 36	29
		6	Day 43	37 to End of DB	43
		DB final visit	Endpoint (DB)	2 to End of DB	
	FU (DB)	7	Day 57	End of DB + 1 to End of FU	10
			Day 15 EW	2 to 22	15
			Day 29 EW	23 to 36	29
			Day 43 EW	37 to 48	43
			Day 57 EW	49 to End of FU	57
NPI-C	DB	2	Baseline (DB)	<=1	1
		4	Day 15	2 to 22	15
		5	Day 29	23 to 36	29
		6	Day 43	37 to End of DB	43
		DB final	Endpoint (DB)	2 to End of DB	
	FU (DB)	7	Day 57	End of DB + 1	10
			-	to End of FU	
			Day 15 EW	2 to 22	15
			Day 29 EW	23 to 36	29
			Day 43 EW	37 to 48	43
			Day 57 EW	49 to End of FU	57
CMAI-C	DB	2	Baseline (DB)	<=1	1
ADAS-Cog-14		4	Day 15	2 to 29	15
		6	Day 43	30 to End of DB	43
		DB final	Endpoint (DB)	2 to End of DB	
GDSI	DB	2	Baseline (DB)	<=1	1
		6	Day 43	2 to End of DB	43
		DB final visit	Endpoint (DB)	2 to End of DB	
MMSE	SCR	1	Screening	<1	
	DB	2	Baseline (DB)	<=1	
		6	Day 43	2 to End of DB	43
		DB final visit	Endpoint (DB)	2 to End of DB	
Weight	SCR	1	Screening	<1	
Labs	DB	2	Baseline (DB)	<=1	1
		DB final visit	Endpoint (DB)	2 to End of DB	
Vital Signs	SCR	1	Screening	<1	
[DB	2	Baseline (DB)	<=1	1
		4	Day 15	2 to 29	15
		6	Day 43	30 to End of DB	43

Table 1- Visit Windows

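### The SAP takes laboratory shifts to the maximum post-baseline value, but its only HDL category is a fall, which needs the minimum; the two rules differ only where repeat values are eligible

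*SAP*

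**What the plan says.** SAP 5.6.3.1 plans two shift tables.

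- **All chemistry:** "Shift in chemisty lab values from baseline to maximum post-baseline value will be summarized for the double-blind phase". No categories are given.
- **Metabolic labs:** "Shift in Metabolic Lab values specifically from baseline to maximum post-baseline value", with listed categories. Those for glucose, triglycerides, total cholesterol and LDL are all rises. The single HDL category is a fall, starting at or above the cut-off: "40 mg/dL to <40 mg/dL (normal to low").

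Neither table has a minimum or worst-direction rule.

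Three other provisions decide how much this matters.

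- **Schedule.** In Protocol 1.3 the row "Hematology, chemistry" is marked at screening, Day 1 and Day 43/early withdrawal, so there is one scheduled post-baseline draw.
- **Repeat draws.** For unscheduled visits that are not administrative, Protocol 4.1 says the "minimum recommended evaluations/assessments include: physical and neurological examinations, vital signs, NPI-C, NPI-12, SDI, C-SSRS, hematology and chemistry laboratory tests". Protocol 7.1 also needs repeat tests for its liver criteria, for example "AST and/or ALT exceeds 5X ULN (confirmed by repeat testing").
- **Visit windows.** SAP 5.1.1 keeps one visit per window: "The other additional visit(s) will not be used in the summaries" or analyses. It then allows the extra visits to be used in determining clinically important endpoints. For labs, the only post-baseline row is Endpoint (DB), from Day 2 to the end of the double-blind phase, with no target day.

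**The concern.** A fall is judged on the lowest value seen and a rise on the highest. The SAP applies the highest to both, so the HDL rule and the HDL category are at odds within one subsection. If a participant has one low and one normal post-baseline value, the table reports no shift.

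Repeat values are most likely in participants seen for a safety event or a change in condition. A shift table should describe those participants correctly. The same reasoning applies to any chemistry analyte for which low is a direction of interest. At stake is the accuracy of a safety description, not an efficacy conclusion.

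**Working it through.** The plan states no figure to reproduce, so the check is one of logic, with a worked example and an assumed illustration.

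**Step 1: the rule.** For a cut-off of 40 mg/dL, max < 40 requires every post-baseline value to be below 40; min < 40 requires only one. With a single value, max = min and the rules agree.

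**Step 2: HDL examples.** Baseline is 45 mg/dL. The shift cut-off is 40 (SAP 5.6.3.1). The markedly abnormal low limit is 35, flagged only if the value is below it (SAP 6.8).

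| Post-baseline values | Maximum rule (SAP) | Minimum rule | Marked low (<35) |
|---|---|---|---|
| 36 | normal to low | normal to low | no |
| 36, 38 | normal to low | normal to low | no |
| 36, 41 | normal to normal | normal to low | no |
| 33, 41 | normal to normal | normal to low | yes |

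The third row is the uncovered case: a fall to between 35 and 40, with another value at or above 40. The fourth row is lost from the shift table but recovered by the markedly abnormal analysis.

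**Step 3: analytes with a low limit.** In the chemistry block of SAP 6.8 these are albumin, bicarbonate, calcium, chloride, glucose, HDL, phosphate, potassium, sodium, total protein and uric acid, 11 in all. For HDL and total protein no high limit is set, so low is the only marked direction.

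**Step 4: how far the rules can diverge (assumed inputs, not from the documents).** Take a participant with two eligible post-baseline values, each with chance *p* of being low and with within-person correlation *r* (bivariate normal).

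- Flagged by the maximum rule: P(both low).
- Flagged by the minimum rule: P(any low) = 2*p* − P(both low).
- Share missed: 1 − P(both low) / P(any low).

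| *p* | *r* | Both low | Any low | Share missed |
|---|---|---|---|---|
| 0.05 | 0 | 0.0025 | 0.0975 | 0.974 |
| 0.10 | 0 | 0.0100 | 0.1900 | 0.947 |
| 0.10 | 0.9 | 0.0689 | 0.1311 | 0.475 |
| 0.20 | 0.9 | 0.1499 | 0.2501 | 0.400 |

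Over *p* from 0.05 to 0.20 and *r* from 0 to 0.9, the share missed runs from 97% down to 40%. It applies only to participants with two eligible values. The documents do not say how many there will be.

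**The case against.** **The window rule may leave one value per participant.** If SAP 5.1.1 governs the shift tables, only one post-baseline visit is kept for labs, the maximum equals the minimum, and changing the rule has no effect. This stands as a real uncertainty, but it does not settle the matter. The word maximum has a purpose only if several values can be eligible, the section leaves a route for extra visits, and the lab row has no target day by which to choose one visit. The text needs to say which values count.

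**A second post-baseline HDL value is not shown.** Protocol Appendix 2 lists HDL in the lipid panel under Other Screening Tests, not under Clinical Chemistry. The unscheduled-visit recommendation names hematology and chemistry, and the liver repeats concern AST, ALT and bilirubin. The SAP plainly expects post-baseline HDL, since it defines a shift and a marked limit, but whether HDL is drawn after baseline, and more than once, needs confirming. This stands.

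**Falls are covered elsewhere.** A reader might infer that low values disappear from the safety reporting. The documents do not support that. SAP 5.6.3.1 tests double-blind values against markedly abnormal limits in both directions, with counts by group and a listing. Protocol 8.2.5 has the investigator review results and record clinically relevant changes as adverse events. Protocol 9.4.3 plans frequency tabulations of abnormalities. What remains is the shift tables, and falls that stop short of the marked limit.

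**Minimum shifts for all chemistry are partly preference.** There is some force in this, because the chemistry sentence defines no categories and the two-sided marked limits exist. For HDL it is not preference, because the SAP itself defines the shift as a fall.

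**Conclusion.** The point holds in a limited form. The stated rule is in the wrong direction for the HDL category, and it cannot show a fall in other chemistry analytes when a normal value is also eligible.

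Size: none with the single scheduled post-baseline draw. With repeat values, a low one drops out of the shift table whenever another post-baseline value is normal. Marked lows are still reported, so for HDL the uncovered range is 35 to below 40 mg/dL. The conclusion assumes that unscheduled or repeat double-blind values can enter the table and, for HDL, that the test is repeated after baseline; the documents settle neither.

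Two stronger readings should be resisted. The 40% to 97% in the illustration is not an estimate of trial impact, because it rests on assumed chances and correlations and applies only to people with two values. Nor can the shift table be called wrong for the trial as a whole: most participants may have one post-baseline value, and unscheduled chemistry is recommended rather than required. This is a minor correction to safety description, and the primary analysis is unaffected.

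**What to change.** In SAP 5.6.3.1:

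1. Define the HDL shift as baseline to the minimum double-blind post-baseline value.
2. For the chemistry analytes with a low limit in SAP 6.8, show the shift to the minimum as well as to the maximum, and state the categories used.
3. State that unscheduled and repeat double-blind values are included in the shift tables, notwithstanding the one-visit-per-window rule in SAP 5.1.1.
4. Confirm against the protocol schedule and Appendix 2 that HDL is collected after baseline. If it is not, remove the HDL shift.

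The cost is a few lines of SAP text and a small programming change, plus some extra table rows. No new data are needed and nothing changes at the sites.

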5.6.3.2. Vital Signs

Continuous vital sign parameters including temperature, weight, pulse, blood pressure (systolic and diastolic), and Body Mass Index (BMI) will be summarized at each assessment time point. Body Mass Index will be calculated as weight $(kg)/(height (m))^2$, at each time point that body weight is measured. The height measurement collected at screening will be used in the calculation. Change from the baseline(DB) will be summarized for the double-blind phase. Descriptive statistics (mean, standard deviation, median, minimum and maximum) will be presented. Abnormality criteria (based on criteria defined below) will be applied to postbaseline values in the double-blind phase. Postbaseline values will be considered treatment-emergent if they meet both value and change criteria in the table below.

For criteria that do not include an increase or decrease from baseline(DB) for the double-blind phase:

- Treatment-emergent will be concluded if the postbaseline value is above the upper limit and the baseline(DB) value is below the upper limit (eg, Normal or Low). The same applies to the postbaseline value being below the lower limit with the baseline value being above the lower limit (eg, Normal or High).
 - If the baseline(DB) value is missing, a postbaseline abnormality will always be considered as TE.

Incidence of treatment-emergent clinically important vital signs during intervention, as defined in Table 4, will be summarized for participants who had a baseline(DB) assessment and at least 1 postbaseline assessment for that vital sign. A listing of participants with treatment-emergent clinically important abnormalities in vital signs will be presented, along with a listing of all vital sign measurements.

Statistical	Analysis	Plan	42847922	ALZ2001
Statistical	a mary sis	1 Iuli	TECTIVEE	

Vital Sign	Abnormal Category	Criteria
Pulse	Abnormally high	$[\geq 100]$ bpm and with $[\geq 15]$ bpm increase from baseline
	Abnormally low	$[\leq 50]$ bpm and with $[\geq 15]$ bpm decrease from baseline
Systolic blood pressure	Abnormally high	[≥180] mm Hg and with [≥20] mm Hg increase from baseline
	Abnormally low	[≤90] mm Hg and with [≥20] mm Hg decrease from baseline
Diastolic blood pressure	Abnormally high	[≥105] mm Hg and with [≥15] mm Hg increase from baseline
	Abnormally low	$[\leq 50]$ mm Hg and with $[\geq 15]$ mm Hg decrease from baseline
Temperature	Abnormally high	[>37.5]°C
	Abnormally low	[<35.5]°C
Weight	Abnormally high	increase [\geq 7%] from baseline
	Abnormally low	decrease [≥7%] from baseline

5.6.3.3. Electrocardiogram

The ECG parameters that will be analyzed are heart rate, PR interval, QRS interval, QT interval, and corrected QT (QTc) interval using the following correction methods: Bazett's formula (QTcB), Fridericia's formula (QTcF).

Bazett's formula: QTcB (msec) = QT (msec) / (RR (msec)/1000)^{1/2}; if RR is missing, use QT (msec) * $(HR(bpm)/60)^{1/2}$;

Fridericia's formula: QTcF (msec) = QT (msec) / (RR (msec)/1000)^{1/3}; if RR is missing, use QT (msec) * (HR(bpm)/60)^{1/3};

Baseline ECG is defined as the average of all ECG results collected up to and including the day of the first dose of study intervention.

The number and percentage of participants with QTc interval increases from average baseline to the maximum postbaseline value will be summarized at each time point for double-blind phase. Refer to the following Table 5 for summary categories.

•	-	8
QTc value (msec)	Normal QTc	\leq 450 for male, \leq 470 for female
		>450 to ≤480 for male, >470 to ≤480 for
		female
		>480 to ≤500
		>500
Clinically significant QTc (msec)	No	≤500
	Yes	>500
QTc change from baseline (msec)	No concern	≤30
	Concern	>30-60
	Clear concern	>60

 Table 5: Criteria for Abnormal QTc Values and Changes From Baseline

Descriptive statistics of ECG parameters and change from average baseline will be summarized at each scheduled time point for double-blind phase.

Abnormality criteria (based on criteria defined in Table 6 below) will be applied to average baseline and postbaseline values.

Statistical Analysis Plan 42847922ALZ2001

Postbaseline abnormalities will be compared with their corresponding average baseline result:

- Treatment-emergent will be concluded if the postbaseline value in the double-blind phase is above the upper limit and the average baseline value is below the upper limit (eg, Normal or Low). The same applies to the postbaseline value being below the lower limit with the average baseline value being above the lower limit (eg, Normal or High).
- If the average baseline value is missing, a postbaseline abnormality in the double-blind phase will always be considered as treatment-emergent.

The number and percentage of participants with treatment-emergent ECG values outside predefined limits will be presented by study intervention over time for DB phase of the study:

	Outside of normal limit if		
ECG Parameter	Abnormally low	Abnormally high	
Heart Rate (bpm)	≤ 50 bpm	≥100 bpm	
PR interval (msec)	≤ 120 msec	≥200 msec	
QRS interval (msec)	≤ 60 msec	≥120 msec	
QT interval (msec)	≤ 200 msec	≥500 msec	
RR interval (msec)	≤ 600 msec	≥1200 msec	

Table 6: Abnormal Limits for ECG Parameters

The interpretation of the ECGs as determined by a central reader will be displayed by the number and percentage of participants meeting the normality criteria. The interpretation will be summarized over time.

A listing of treatment emergent clinically relevant ECG abnormalities will also be provided.

